5.1 Design

Aim 2 of this research study is to design and pilot test a method for collecting data on storage device use among patients and visitors who accept firearm safety materials or are interested in receiving a firearm storage device shipped to their address. The study design is an iterative pilot test of survey data collection methods and determination of scalability and feasibility for distribution of firearm storage devices. The study population and sample will be (a) individuals who are patients or visitors to PAH who are screened

for a firearm, screen positive, and accept a firearm safety brochure and storage device OR (b) individuals interested in receiving a firearm storage device and self-scan the unique QR code on the study poster in the entry hall of PAH with minimal or no security supervisor engagement. A unique QR code linking directly to the initial survey will be embedded into the firearm safety brochure as well as the poster in the entry hall of PAH next to the distribution area. Individual group (a) will be informed by security that survey participation is optional, but that it is helpful for our efforts, and that participation will be compensated with a \$10 Amazon gift card for the initial survey and a \$20 Amazon gift card for completing the follow-up survey. Individual group (b) will not be actively engaged by security, and will self-enroll in the study by viewing the posted signage and completing the QR code linked survey. Individuals who decline the device will also be eligible for the initial survey via the poster QR code, but they will not be eligible for the follow-up survey.

The primary outcome measure is survey response rate: whether an eligible visitor or patient completed the firearm storage survey after accepting firearm safety materials or after scanning the QR code on the poster. This will be measured through Qualtrics survey completion rate and PAH Evolv security system foot traffic. We will use the survey completion rate as the numerator and the number of people scanning positive for a firearm as the denominator for this rate.

The secondary outcome measures are from initial and follow-up survey responses: (1) firearm storage behavior, (2) likelihood of using cable lock within the next week (extremely unlikely to extremely likely scale). These outcomes are directly tied to questions asked in both surveys.

Lastly, as exploratory outcomes, we will compare survey response rates between several different variations of survey distribution: web survey accessed via QR code posted in the entry hall; web survey accessed via QR code included on the safety brochure; follow-up survey link administered by text message.

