3.1 Primary outcome

The primary outcome measure is survey response rate: whether an eligible visitor or patient completed the firearm storage survey after accepting firearm safety materials or after scanning the QR code on the study poster.

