3.3 Exploratory outcomes

To compare survey response rates between several different variations of survey distribution: web survey accessed via QR code posted in the entry hall; web survey accessed via QR code included on the safety brochure; follow-up survey link administered by text message.

4. Background

Firearm injury is the leading cause of death of children in the U.S. and Philadelphia (3). Our work shows unintentional injuries are the leading cause of nonfatal firearm injuries with rates disproportionately higher in Black communities (Figure 1). As in Philadelphia, forty percent of American adults live in a household with at least one firearm, and two thirds of these have at least one firearm that is unlocked (4–6). Secure storage of firearms can prevent youth suicide, unintentional injury, intimate partner homicide, theft, and violent crime (7–10). Education and legislation have had limited impact on promoting safe firearm storage (11–15).

[figure not shown]

Figure 1: Annual U.S. Firearm Injury Rates per 100,000 by Intent, Age, Race, and Ethnicity, 2019-20 (Kaufman...Delgado, under review)

Penn Medicine prohibits firearms within its buildings. In November 2021, Penn Medicine implemented the Evolv weapons detection system in entrances to Pennsylvania Hospital and its medical office buildings (2). In the first 5 months of the program, there were over 300,000 screening encounters and 408 firearms identified and stored by hospital security. In July 2022 our team piloted an innovative program in which security guards offer a firearm cable lock and safety brochure when the gun owner return to retrieve their firearm at the conclusion of their visit. To date, 47% of patients and visitors who stored their firearm with security have taken a cable lock when offered, resulting in over 300 firearm safety locks and brochures distributed to firearm owners.

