5.3 Target populations

Pennsylvania Hospital visitors and patients who (a) screen positive for carrying a firearm and who accept a firearm safety brochure and storage device OR (b) are interested in receiving a firearm storage device and self-select to complete the initial QR code survey linked on the study poster.

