5.4 Accrual

This is an evaluation of data collection methodologies. We will assess response rates every (1) week and tabulate responses on the acceptability of data collection methods. We will iteratively refine data collection methods over the course of 6 months to achieve the highest possible response rate.

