5.5 Key inclusion criteria

Individuals who are visitors or patients at Pennsylvania Hospital, are identified through the Evolv system as carrying a firearm, and who accept firearm safety materials OR any patient or visitor interested in receiving a firearm storage device who self-selects into the study by scanning the QR code on the study poster. For eligibility of the follow-up survey, participants must have responded yes to taking a cable lock

in the initial brochure survey or yes to receiving a firearm storage device shipped to their address from the poster survey.

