2. Have you used the firearm storage device from Penn Medicine to secure your firearm? [Yes/No]
3. Have you made any other changes in your firearm storage? [write in]

Iterative Analysis and Refinement of Data Collection Methods: We will assess response rates every (1) week and tabulate responses on the acceptability of data collection methods. We will iteratively refine data collection methods over the course of 6 months to achieve the highest possible response rate. The participant data collected will be their phone number and/or their address for individuals completed the survey via the study poster. No identifying information or demographics will be collected to uphold anonymity. Cell phone number will be used to distribute the gift card via the Nudge Unit’s Google Voice account and re-contact with invitation to participate in the follow-up survey. Their address will only be used to ship the firearm storage device to individuals who self-enrolled in the study via the study posters.

9. Analysis plan

The primary outcome is survey response rate. This will be monitored via Qualtrics by looking at response volume by week. These responses will be compared to security department reports on the number of firearms identified/stored to allow us to calculate the proportion of eligible individuals who responded per week. The secondary outcome measures are: (1) firearm storage behavior among a) locked safe/gun cabinet, b) trigger lock or cable lock, c) unsecured, d) other (write in), (2) likelihood of using cable lock within the next week (extremely unlikely to extremely likely scale).

10. Human research protection

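### The primary response rate counts poster completions from any interested patient or visitor but divides by firearm-positive people, so it is not a response rate among eligible people.

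*Protocol*

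**What the plan says.** Section 3.1 makes survey response rate the primary outcome. It is met by anyone eligible who "completed the firearm storage survey after accepting firearm safety materials or after scanning the QR code on the study poster". Both routes therefore count.

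Section 5.1 names Qualtrics completions and Evolv foot traffic as data sources, then fixes the calculation: the "survey completion rate as the numerator and the number of people scanning positive for a firearm as the denominator for this rate". The Detailed Description for ClinicalTrials.gov repeats this. Section 9 takes the denominator from "security department reports on the number of firearms identified/stored to allow us to calculate the proportion of eligible individuals who responded per week".

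The poster route needs no positive screen. Section 5.3 describes its users as people who "are interested in receiving a firearm storage device and self-select to complete the initial QR code survey linked on the study poster", and section 5.5 admits "any patient or visitor interested in receiving a firearm storage device who self-selects into the study by scanning the QR code". Section 5.1 adds: "Individual group (b) will not be actively engaged by security, and will self-enroll in the study by viewing the posted signage".

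On use of the results, section 5.4 provides for weekly assessment of response rates and states: "We will iteratively refine data collection methods over the course of 6 months to achieve the highest possible response rate".

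**The concern.** A response proportion needs every counted responder to belong to the group in the denominator. Here a poster respondent who did not screen positive is eligible and is counted, but is absent from the denominator. The ratio can rise because more passers-by use the poster while response among people handed a brochure stays flat or falls.

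A rise in poster completions is a real result, since the poster is itself under test. The fault is that this ratio presents it as response among firearm-positive people and mixes it with brochure response. Because methods are to be adjusted during the 6 months in pursuit of a higher rate, separating the routes at the end would not undo choices made on a misleading figure.

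A secondary point is that the denominator can include firearm-positive people who never received a brochure, such as those who choose to leave with their weapon (section 1). Their number is not given.

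**Working it through.** The protocol states no target rate or sample size, so there is no figure of its own to reproduce. The definitions settle the point; the arithmetic only shows scale.

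**Definitions side by side**

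| Group | In numerator if they complete? | In denominator? |
|---|---|---|
| Screened positive, accepted materials (5.5) | Yes | Yes |
| Screened positive, declined the device, used the poster (5.1, 8.2) | Yes | Yes |
| Not screened positive, used the poster (5.3, 5.5) | Yes | No |

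The third row breaks the proportion. Two wording faults add to it: section 5.1 puts a rate where a count of completed surveys belongs, and the denominator is people in 5.1 but firearms in 9.

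**Inputs.** Section 4 gives the volumes: "In the first 5 months of the program, there were over 300,000 screening encounters and 408 firearms identified and stored by hospital security". It also gives 47% cable lock acceptance. Assumptions: these figures continue, one firearm is one person, and lock acceptance stands for acceptance of materials. Brochure response and poster uptake are not in the protocol and are varied.

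**Effect of one poster completion a week**

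- Positives per week: 408/5 = 81.6 a month; 81.6 × 12/52 = 18.8.
- One completion: 1/18.83 = 5.3 points. Two add 10.6 and three add 15.9.
- With 10 positives a week: 1/10 = 10.0 points. With 30: 1/30 = 3.3 points.

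**Six-month ratio**

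- Positives D = 81.6 × 6 = 489.6, about 490.
- Acceptors = 0.47 × 489.6 = 230.1, about 230.
- Ratio = (r × 230.1 + P)/489.6, where r is the assumed brochure response among acceptors and P is the number of poster completions.

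| r | P = 0 | P = 50 | P = 100 |
|---|---|---|---|
| 10% | 4.7% | 14.9% | 25.1% |
| 25% | 11.8% | 22.0% | 32.2% |
| 50% | 23.5% | 33.7% | 43.9% |

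Within each row, brochure response is constant; only the poster moves the result. At r = 25% the ratio reaches 100% when P = 489.6 − 0.25 × 230.1 = 432. With P = 0 it cannot exceed 47%, even if every acceptor responds.

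**Gap between the populations.** 408/300,000 = 0.136% at most, since encounters exceed 300,000; that is 300,000/408 = 735 encounters per stored firearm. Encounters are not distinct people, they include the medical office building entrances, and most people would not be interested. The figure shows how much wider the poster's audience is than the denominator. It does not predict poster volume.

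**The case against.** The strongest reply is that this is an iterative pilot with no target rate or test, and that the routes can be told apart: each has its own QR code and the poster survey has a re-worded question. Sections 3.3 and 5.1 already plan an exploratory comparison of response by route, and section 9 already monitors weekly response volume. No passage says that one pooled ratio drives the weekly decisions; section 5.4 speaks of response rates in the plural and also of acceptability. All of this is true, and the use of the pooled ratio for refinement is an inference. It remains that the primary definition itself is wrong, and an exploratory comparison does not change it.

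Some poster users will be firearm-positive: the poster hangs beside the distribution area, and device decliners may use it. That stands. If half of poster completers had screened positive, the part coming from outside the denominator would be 0.5 × 5.3, about 2.7 points per weekly completion. Device decliners are no part of this objection. People who leave with their weapon could likewise use the poster if interested, which weakens the secondary point.

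The check for imposter participants in section 10.1 compares completions with daily cable lock distribution. It might flag a large surge, which makes ratios above 100% less likely in practice. It supplies no denominator for poster respondents and could flag genuine ones.

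**Conclusion.** The concern holds. As written, the sole primary outcome is not the share of eligible people who responded. Its numerator admits people whom its denominator excludes, and no passage limits the numerator to brochure completions. This follows from the definitions alone.

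The size depends on poster uptake and on how many poster completers also screened positive; neither is given. At historical volume, a few poster completions a week would move the weekly figure by 5 to 16 points with no change in brochure response. That is large enough to mislead decisions about which collection method works. The definition should be corrected before the rate is used or reported.

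**What to change.** In sections 5.1 and 9 and the registry text, stop dividing poster completions by firearm-positive people or by firearms. Section 3.1 states no denominator and needs only to name the separate measures. Use the number of completed surveys as numerator, and report by route and week:

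- **Brochure:** completions through the brochure code divided by people given a brochure, from a security tally.
- **Poster:** the weekly count of completions through the poster code, plus completions divided by poster-survey opens. Label the second as completion among those who scanned, because it measures drop-out after opening and not reach. State how repeat scans are handled.
- **Reach, optional:** brochure completions per firearm-positive person, labelled as reach.

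State which measure guides refinement, for example the brochure rate for changes to the brochure route and the weekly count for changes to the poster.

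The cost is protocol and registry wording and a weekly tally of people given a brochure. Section 4 reports a running total of locks and brochures distributed, so some count exists, but the security reports named in section 9 cover firearms only. Poster-survey opens are assumed to be available from Qualtrics. The study gives up a single pooled rate.

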5.2 Study duration

The aim of this study is expected to take 8 months including planning, 6-month active phase of the study, and then analysis and dissemination of results.

Activity	Month 1	Month 2	Month 3	Month 4	Month 5	Month 6	Month 7	Month 8	Month 9	Month 10	Month 11	Month 12
Aim 1												
IRB approval	Blue											
Data collection & analysis		Blue	Blue									
Manuscript				Blue	Blue							
Aim 2												
IRB approval	Green											
Initial design	Green											
Iterative data collection		Green	Green	Green	Green	Green						
Aim 3												
Lockbox vendor contract					Yellow	Yellow	Yellow					
IRB approval								Yellow				
Direct lockbox distribution									Yellow			
Lockbox voucher distribution										Yellow		
Lockbox shipping distribution										Yellow		
Analysis, manuscript, network dissemination											Yellow	

5.3 Target populations

Pennsylvania Hospital visitors and patients who (a) screen positive for carrying a firearm and who accept a firearm safety brochure and storage device OR (b) are interested in receiving a firearm storage device and self-select to complete the initial QR code survey linked on the study poster.

5.4 Accrual

This is an evaluation of data collection methodologies. We will assess response rates every (1) week and tabulate responses on the acceptability of data collection methods. We will iteratively refine data collection methods over the course of 6 months to achieve the highest possible response rate.

5.5 Key inclusion criteria

Individuals who are visitors or patients at Pennsylvania Hospital, are identified through the Evolv system as carrying a firearm, and who accept firearm safety materials OR any patient or visitor interested in receiving a firearm storage device who self-selects into the study by scanning the QR code on the study poster. For eligibility of the follow-up survey, participants must have responded yes to taking a cable lock

in the initial brochure survey or yes to receiving a firearm storage device shipped to their address from the poster survey.

5.6 Key exclusion criteria

None.

6. Subject recruitment

Since this aim is a trial of data collection methods within an existing hospital program, individuals will not be recruited or enrolled individually, but instead eligible individuals will be offered the option to participate in the survey upon receipt of firearm safety materials or self-selection via scanning the QR code linked to the initial study survey. The former option will be presented to individuals alongside the existing distribution workflow of the program.

7. Subject compensation

Total potential compensation per participant is \$30 in the form of Amazon gift cards. Individuals will receive a \$10 Amazon gift card for completing the initial survey. If participants choose to complete the follow-up survey, they will receive a \$20 Amazon gift card. The gift card will be shared manually via text message with the participants within 1-2 weeks of survey completion. Participants who elect to have a firearm storage device shipped to their address will receive a free device (either a cable lock and/or lock box).

8. Study procedures

If participants agree to participate in the survey, they will continue forward in the survey. If participants disagree with the terms and consent statement, they will not be able to progress in the survey and no additional information will be collected from the individual.

8.2 Procedures

Study procedure. A unique QR code linking directly to the survey will be embedded into our firearm safety brochure and study poster available in the entry hall of PAH. Participants who scan positive for a firearm and are offered safety materials (inclusive of the brochure) will be informed that survey participation is optional, but that it is helpful to our efforts, and that participation will be compensated with a \$10 Amazon gift card for completing the initial survey and a \$20 Amazon gift card for completing the follow-up survey. Individuals who decline the device will also be eligible for the initial survey via the poster QR code. Gift cards will be distributed digitally via text in accordance with the participants consent to share their phone number. Only eligible participants will receive a text with a link to complete the optional follow-up survey.

Participants who self-select into the study via the study poster will be linked to the initial survey in Qualtrics with one re-worded question based on context. Individuals will receive \$10 Amazon gift card for completing the initial survey and a \$20 Amazon gift card for completing the follow-up survey. Only eligible participants will receive a text with a link to complete the optional follow-up survey.

Initial Survey via Brochure. Upon scanning the QR code on the brochure, an individual will be brought directly to the initial Qualtrics survey. The first question of the survey is a statement outlining that the individual's participation is voluntary and informed. The individual must select agree or disagree before proceeding with the survey. If the individual chooses to agree, they will then begin the initial survey. After completion of the survey, they will receive a text message with their Amazon giftcard information within 1-2 weeks. The text will read, "Hello, this is Penn Medicine. Thank you for participating in our survey. As an appreciation for your time, please see below for your gift card information: [INSERT GIFT CARD #]"

This initial survey will focus on the following elements. Survey language may be refined during the research process:

- 1.
2. To receive an Amazon gift card and participate in future follow-up surveys, please enter your phone number.
3. Most recent visit to Penn Medicine (mm/dd/yyyy)
4. Did you get a cable lock today?
 - a. Yes
 - b. No
5. [IF NO #3] What's the reason you didn't accept one?
 - a. Already have one
 - i. [LOGIC] How often do you use it?
 1. Every time I store my device
 2. Almost every time I store my device
 3. Almost never when I store my device
 - ii. [LOGIC] What's your preference for storing your firearm? [text field]
 - b. Prefer different storage device
 - i. [LOGIC] Which of the following storage devices would you prefer?
 1. Lock box
 2. Trigger lock
 3. Gun safe
 4. Calmshell / "life jacket"
 5. Gun cabinet
 6. In-vehicle lock
 7. Other/key/PIN/biometric (please specify):
 - c. Don't want one
 - d. Not offered or not available
6. [IF YES #3] If you have accepted a device today, how likely are you to use it in the next week?
 - a. Extremely likely
 - b. Somewhat likely
 - c. Neither likely nor unlikely
 - d. Somewhat unlikely
 - e. Extremely unlikely
7. How do you usually store your firearm?
 - a. In a locked safe or gun cabinet
 - b. With a trigger lock or cable lock
 - c. Unlocked (not secured with a lock, in a locked container, or not stored in a locked cabinet)
 - d. Other (please specify)

Initial Survey via Poster. Upon scanning the QR code on the poster next to the distribution area, an individual will be brought directly to the initial Qualtrics survey. The first question of the survey is a statement outlining that the individual's participation is voluntary and informed. The individual must select agree or disagree before proceeding with the survey. If the individual chooses to agree, they will

then begin the initial survey. After completion of the survey, they will receive a text message with their Amazon giftcard information within 1-2 weeks. The text will read, "Hello, this is Penn Medicine. Thank you for participating in our survey. As an appreciation for your time, please see below for your gift card information: [INSERT GIFT CARD #]"

This initial survey will focus on the following elements. Survey language may be refined during the research process:

1. To receive an Amazon gift card and participate in future follow-up surveys, please enter your phone number.
2. Most recent visit to Penn Medicine (mm/dd/yyyy)
3. Are you interested in receiving a firearm storage device shipped to your address?
4. [IF NO #3] What's the reason you don't want one?
 - a. Already have one
 - i. [LOGIC] How often do you use it?
 1. Every time I store my device
 2. Almost every time I store my device
 3. Almost never when I store my device
 - ii. [LOGIC] What's your preference for storing your firearm? [text field]
 - b. Prefer different storage device
 - i. [LOGIC] Which of the following storage devices would you prefer?
 1. Lock box
 2. Trigger lock
 3. Gun safe
 4. Calmshell / "life jacket"
 5. Gun cabinet
 6. In-vehicle lock
 7. Other/key/PIN/biometric (please specify):
 - c. Don't want to share my address
 - i. [LOGIC] Please select which of the following you'd be open to:
 1. Returning to Penn Medicine to pick up a free cable lock
 2. Receiving a free cable lock locally
 3. Other (please specify)
5. [IF YES #3] What is the best US shipping address for you?
 - a. [Text box fields for street, apt, city, zip, name]
6. How do you usually store your firearm?
 - a. In a locked safe or gun cabinet
 - b. With a trigger lock or cable lock
 - c. Unlocked (not secured with a lock, in a locked container, or not stored in a locked cabinet)
 - d. Other (please specify)
7. Once you receive your cable lock, how likely are you to use it in the next week?
 - a. Extremely likely

- b. Somewhat likely
- c. Neither likely nor unlikely
- d. Somewhat unlikely
- e. Extremely unlikely

Follow-up Survey: Participants who complete the initial survey and who agree to provide contact information will be contacted via text message 1 month after enrollment for a follow-up survey that adds questions about if and how participants have changed their storage behavior. The text language will read:

“Hello, this is Penn Medicine. Thank you for completing our initial survey. If you’re interested in taking the follow-up survey, please click the survey link below: [INSERT LINK]”

Participants will receive the second Amazon gift card incentive 1-2 weeks after completion of this survey. “Hello, this is Penn Medicine. Thank you for participating in our survey. As an appreciation for your time, please see below for your gift card information: [INSERT GIFT CARD #]”

The follow-up survey questions are subject to be amended based on the principal investigators’ discretion. Eligible participants from the initial survey, those who answered yes to accepting a cable lock, will be asked the following questions to understand if their behavior changed:

1. Since you’ve visited Penn Medicine, how have you stored your firearm? [option selection]
 - a. Participants select [a] in a locked safe or gun cabinet, b) with a trigger lock or cable lock, c) unlocked (not secured with a lock, in a locked container, or not stored in a locked cabinet), d) other (please specify) with an open comment box]
2. Have you used the firearm storage device from Penn Medicine to secure your firearm? [Yes/No]
3. Have you made any other changes in your firearm storage? [write in]

Iterative Analysis and Refinement of Data Collection Methods: We will assess response rates every (1) week and tabulate responses on the acceptability of data collection methods. We will iteratively refine data collection methods over the course of 6 months to achieve the highest possible response rate. The participant data collected will be their phone number and/or their address for individuals completed the survey via the study poster. No identifying information or demographics will be collected to uphold anonymity. Cell phone number will be used to distribute the gift card via the Nudge Unit’s Google Voice account and re-contact with invitation to participate in the follow-up survey. Their address will only be used to ship the firearm storage device to individuals who self-enrolled in the study via the study posters.

9. Analysis plan

The primary outcome is survey response rate. This will be monitored via Qualtrics by looking at response volume by week. These responses will be compared to security department reports on the number of firearms identified/stored to allow us to calculate the proportion of eligible individuals who responded per week. The secondary outcome measures are: (1) firearm storage behavior among a) locked safe/gun cabinet, b) trigger lock or cable lock, c) unsecured, d) other (write in), (2) likelihood of using cable lock within the next week (extremely unlikely to extremely likely scale).

10. Human research protection

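### The poster form is described as the brochure form with one re-worded question, but the two listed forms differ in five places, and three of the resulting gaps damage the data

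*Protocol*

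**What the plan says.** Section 8.2 states that people who self-select through the poster "will be linked to the initial survey in Qualtrics with one re-worded question based on context", and then lists both forms item by item.

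- The brochure form opens its device block with "Did you get a cable lock today". A no leads to a reason item and a yes leads to "If you have accepted a device today, how likely are you to use it in the next week". Usual storage comes last.
- The poster form asks instead "Are you interested in receiving a firearm storage device shipped to your address". A no leads to a reason item and a yes to an address item. Usual storage follows, and the form ends with "Once you receive your cable lock, how likely are you to use it in the next week".

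Three other parts of the protocol bear on this. Sections 5.1 and 8.2 let people who decline the device answer the initial survey through the poster code. Section 5.5 ties follow-up eligibility to a yes on taking a lock (brochure) or a yes on shipping (poster). Sections 3.2, 5.1 and 9 define the secondary outcomes, usual storage and likelihood of use within a week, once for the whole study, without separating the channels.

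**The concern.** A reader who relies on the one-question sentence will treat the two forms as one instrument and their answers as interchangeable. If the forms differ in who is asked a question, which answers are offered, or which facts are recorded, then the secondary outcomes have a different meaning in each channel. Some of that loss is beyond repair at analysis: a fact that was never asked, or an answer that was never offered, cannot be recovered by any analysis plan.

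**Working it through.** The only figure to reproduce is the stated number of changes, which is 1. The inputs are the two item lists in section 8.2.

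| Element | Brochure form | Poster form | Needed for shipping? |
|---|---|---|---|
| Phone number; date of latest visit | items 2, 3 | items 1, 2 | identical |
| Gate | item 4, "Did you get a cable lock today" | item 3, "Are you interested in receiving a firearm storage device shipped to your address" | yes; presumably the one change admitted |
| Reason for a no | item 5, "What's the reason you didn't accept one"; options: already has one, prefers another device, does not want one, "Not offered or not available" | item 4, "What's the reason you don't want one"; options: already has one, prefers another device, unwilling to give an address (with a nested question) | partly |
| Address | none | item 5, on yes | yes |
| Likelihood of use | item 6, on yes only, "If you have accepted a device today, how likely are you to use it in the next week" | item 7, no branch printed, "Once you receive your cable lock, how likely are you to use it in the next week" | wording yes, missing branch no |
| Usual storage | item 7, after likelihood | item 6, before likelihood; same wording | no |

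**Count.** Gate, reason, address, likelihood and order make 5. Splitting the reason item into stem and options, and the likelihood item into wording and branch, gives 5 + 2 = 7. Taking away the admitted gate change leaves 4 or 6. The stated figure of 1 is not reproduced on any count. The blank first brochure item, the numbering offset and the missing yes/no options under the poster gate were left out of the count, because they may come from text extraction.

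**(a) Missing answer.** Take someone who declines the device, scans the poster as sections 5.1 and 8.2 allow, and answers no to shipping. The three reasons offered are ownership, a preference for another device, and unwillingness to give an address. A free-text other appears only beneath the last two. A person who simply wants no device has no true answer.

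**(b) Unrecorded lock.** Take someone who accepts a lock on site and scans the poster, which hangs beside the distribution area.
- If they answer yes to shipping, they look like anyone else requesting a device.
- If they answer no, the nearest reason is that they already have one, which cannot be told apart from prior ownership. They also fail the section 5.5 follow-up criterion for the poster, although they hold a device from the programme.
- The follow-up text in section 8.2 describes eligible people as those who said yes to accepting a cable lock. The poster form does not ask that.

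**(c) Two bases for secondary outcome 2.** On the brochure, the base is people who took a lock that day, and the week runs from that day. On the poster, no branch is printed and the lock has yet to arrive, so people who declined shipping may be asked too. Let d be the share of poster likelihood answers that come from people who declined shipping. Let p_R and p_D be the proportions answering likely among those who requested and those who declined a device. The poster result is then (1 − d)·p_R + d·p_D, which differs from p_R by d·(p_D − p_R). The protocol gives none of these quantities, so the difference has no computable size. It is zero only if nobody who declined is asked, or if the two groups answer alike.

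**The case against.** The strongest case on the other side has four parts.

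- **Several differences follow from context.** The gate change is the one the protocol admits. An address is needed to ship a device. The option "Not offered or not available" does not fit a question about shipping, and a person awaiting delivery cannot be asked about a device in hand. All of this stands. It reduces the list of faults but does not explain (a), the absence of any question about an on-site lock, the missing branch or the reversed order.
- **The lists are provisional.** Section 8.2 allows survey language to be refined, and the study is an iterative pilot. That covers changes over time. It does not reconcile a sentence with two lists printed in the same version.
- **The poster likelihood wording presupposes delivery, so a branch may be intended.** That is possible, but conditional items on both forms carry a printed condition and this one does not.
- **A statistical analysis plan could report by channel.** That is so, and pooling of the secondary outcomes is only implied by their single definition. It would help with (c) but not with (a) or (b).

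A reader might also infer that item order biases the planned comparison of channels. The documents do not support that. The exploratory outcome in section 3.3 compares response rates, not answers, and the order of the last two items has little bearing on whether a form is completed. No comparison of likelihood between channels is planned, and the documents give neither the size nor the direction of any order effect. Nor was a general other option dropped: the brochure reason list has none at its top level either.

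**Conclusion.** The contradiction holds: one change is stated, and five are found on a coarse count (seven on a fine count). Three consequences matter. People who decline a device may have no true answer on the poster. Locks taken on site are not recorded there, which also affects follow-up eligibility. And secondary outcome 2 rests on two different bases and reference points, so a combined figure would not estimate one quantity. The reversed order is a lesser, avoidable mismatch. The point does not reach the planned comparison of response rates by way of item order, and no shift in percentage points can be put on it. It assumes that the forms are run as printed and that some on-site lock-takers and some people who declined a device use the poster. The protocol allows the latter expressly, and the poster's position makes the former plausible. It should be corrected, but it does not undermine the primary outcome.

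**What to change.** On the poster form, add one yes/no item on whether a lock was received at this visit, and restore the answer for not wanting a device. On both forms, put usual storage and likelihood in the same order, and ask likelihood under one stated branch rule: only of those who received or requested a device. The branch matters, because moving likelihood into a common block without it would keep the fault and extend it to brochure respondents who took no lock. Keep the address items on the poster only. Report secondary outcome 2 by channel before any pooling. Correct the one-question sentence so that it lists the real differences, and have section 5.5 and the follow-up text say whether a poster respondent who took a lock on site is eligible for follow-up.

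The cost is reprogramming, mainly of one form, and one added item. The protocol does not say whether collection has begun; if it has, responses should carry a form-version flag.
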